If there is (1) a steroid refractory GVHD or (2) graft failure in cohort 2, then the study will stop.

The secondary aim is to determine if there is evidence of disease response to IAC. If there is evidence of disease response in either arm, additional studies will be planned.

f) Study Variables

• *Independent Variables or Interventions*

IAC infusion every 8-12 weeks as tolerated and feasible.

Toxicity will be measured by occurrence of any experimental treatment-related Adverse Events (AE) up to 12 weeks of completion of therapy. The CTCAE Version 4.0 will be utilized for the description and grading of the AE. All symptoms, signs, or diseases assessed as experimental treatment-related will be captured and graded by a study investigator and an attribution will be associated to the experimental therapy (IAC).

Attribution of the AE:

- Definite – The AE is clearly related to the experimental therapy
- Probable – The AE is likely related to the experimental therapy
- Possible – The AE may be related to the study treatment
- Unlikely – The AE is doubtfully related to the study treatment
- Unrelated – The AE is clearly NOT related to the study treatment

Any experimental treatment-related irreversible grade 3 or higher AE (definite, probable or possible) will result in that patient not receiving any further treatment. If the AE corrects completely or to Grade 1 within 2 weeks, repeat treatment as directed by protocol may be utilized. If there is more than one such irreversible experimental treatment-related Grade 3 adverse event, the study will be terminated for that cohort.

Since a major concern is that the IAC might trigger an immune response that results in steroid-refractory GVHD OR graft failure (in cohort 2), specific parameters to diminish the likelihood of these events are included in the inclusion criteria (e.g. durable engraftment and high donor chimerism). Furthermore, the study will be terminated if even a single episode of these events occurs.

Overall response rate will be defined as the proportion of patients meeting the criteria for partial response (PR), very good partial response (VGPR) and complete response (CR). Disease response will be determined by Standards of Blood and Marrow Transplant Program disease-specific parameters.

- *Dependent Variables or Outcome Measures*

Toxicity and disease response will be measured. Disease response will use standard disease-specific parameters.

g) Drugs/Devices/Biologics

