The infusion of irradiated cells may be associated with short-term effects such as fevers, chills, dyspnea and systemic inflammatory symptoms such as shortness of breath due to pneumonia or diarrhea due to colitis. Long-term effects may include infection or autoimmunity. For patients who have received an allogeneic transplant the manifestation of "autoimmunity" might be graft-versus host disease or graft rejection.

(b) Risk Of Imposing An Intervention On Subject With Existing Condition

N/A

(c) Other Foreseeable Risks

The patients receiving therapy with IAC have very high-risk diseases and are receiving IAC as an adjuvant to transplant therapy. It may be hard to determine the toxicity related to their disease, standard treatment (transplant therapy) or the experimental therapy (IAC). In this context all patients will be at risk for infection, bleeding, organ toxicity (including heart, lung, kidney, liver, oropharyngeal, gastrointestinal, neurologic, ophthalmic and bone marrow) some of which might be irreversible and some of which could lead to long-term morbidity and death. These risks are intrinsic to the disease and standard therapy and may be worsened by the experimental therapy.

(d) Observation And Sensitive Information

N/A

(5) Minimizing Risks

The experimental intervention (IAC) involves administration of irradiated Patients receiving IAC will be reviewed weekly at 2 meetings – a weekly transplant meeting and a weekly clinical research meeting. Any SAE considered likely related to IAC will be discussed and presented for biometric evaluation re:stopping rules.

(6) Certificate of Confidentiality

N/A

(7) Potential Benefits to Subjects

IAC may improve clinical outcomes by increasing disease response rates and disease control.

(8) Provisions to Protect the Privacy Interests of Subjects

Patient confidentiality will be strictly maintained according to NIH guidelines.

(a) Research Team Access To Subject Data

The subject's personal health information, identifiers and research data are stored and kept in a secure area in the [REDACTED] computer screens containing personal health identifiers are inaccessible to public view. Only the study doctor and research team will have direct access.

c) Secondary Data – Records/Chart Reviews/Databases/Tissue Banks/etc.

[REDACTED]

20

RESERVED FOR IRB STAMP
DO NOT MODIFY THIS SPACE

Form V

Approval Date:
Expiration Date:

4/23/2021
4/22/2022

N/A

Chart/Record Review Selection

N/A

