The data collected will be stored on clinical trial management software - Oncore in Principal Investigator's computer. All Computers in OHRs are encrypted, password protected and on secured servers. Only the Principal Investigator and/or the research team will have access to the patient's data.

c) Data and Safety Monitoring

Minimal risk is anticipated however there is always the possibility of unanticipated effects. Institutional Data Safety Monitoring Board/ HROC will monitor the data from the research after initial 2-3 patients and based on their suggestions the research will be conducted as is/ Modified or discontinued.

▪ Periodic Data Evaluation

Weekly at the Blood & Marrow Transplantation and Hematologic Malignancies Tumor Study group research meetings.

▪ Type of Data Evaluated

Treatment related toxicities; unanticipated adverse events.

▪ Collection of Safety Information

Patient safety data will be reviewed at both of the above cited weekly meetings.

▪ Frequency Of Data Collection

Weekly. If there is no weekly meeting (e.g. holiday) data will be delayed until the next scheduled meeting.

▪ Reviewer of Data

Principal Investigator reviews all data.

▪ Schedule Of Review Of Cumulative Data

Review of cumulative data will occur weekly at the Hematologic Malignancies Tumor Study Group weekly research meeting.

- **Tests for Safety Data**

Weekly meetings of the Blood & Marrow Transplant Program and Hematologic Malignancies Clinical Research Tumor Study Group review each patient. Experimental treatment-related SAEs will be reported for biometric review.

- **Suspension of Research**

Suspension will take place based upon stopping rules

d) Reporting Results

- **Sharing of Results with Subjects**

Clinical results can only be shared following completion of the study.

- **Individual Results**

Patients will be notified of any abnormal findings or lab results.

- **Aggregate Results**

N/A

- **Professional Reporting**

It is expected that the results of this process will be submitted for publication in a timely manner following the conclusion. [REDACTED] all co-authors prior to submission or use, will review any abstract or manuscript.

- **ClinicalTrials.Gov Registration And Data Reporting**

The study will be registered in accordance to applicable institutional guidelines.

7) Data and/or Specimen Banking

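### The one board review specified comes after the first 2-3 patients in the study rather than in each cohort, and the trigger for biometric review does not match the events the stopping rule counts

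*Combined protocol and SAP*

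**What the plan says.** **Board review.** Section 6c, Data and Safety Monitoring, says that the institutional board "will monitor the data from the research after initial 2-3 patients", and that "based on their suggestions the research will be conducted as is/ Modified or discontinued". No other board review is scheduled, and cohorts are not mentioned. The rest of section 6c describes weekly review by the transplant and tumor study groups, with the principal investigator reviewing all data.

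**The risk singled out.** Section f), Study Variables, states that "a major concern is that the IAC might trigger an immune response that results in steroid-refractory GVHD OR graft failure" in Cohort 2. Sections e) and f) both stop the study after a single such event.

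**Referral for biometric review.** There are two versions:
- Minimizing Risks: "Any SAE considered likely related to IAC will be discussed and presented for biometric evaluation re:stopping rules".
- Section 6c, Tests for Safety Data: "Experimental treatment-related SAEs will be reported for biometric review".

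**What the toxicity rule counts.** Section f) says: "Any experimental treatment-related irreversible grade 3 or higher AE (definite, probable or possible) will result in that patient not receiving any further treatment". It then says: "If there is more than one such irreversible experimental treatment-related Grade 3 adverse event, the study will be terminated for that cohort". I read *such* as carrying the same attribution grades into the cohort-level rule.

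**The concern.** The board review is the one point at which a body other than the study team is scheduled to decide whether the trial continues, changes or stops. Because it is tied to the first patients in the study, it can take place before anyone in Cohort 2 has been treated, and Cohort 2 carries the risk that the protocol singles out. No later board review is planned to fill that gap.

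The second issue is a mismatch of definitions. In the section f) attribution scale, *likely* is the word used to describe the Probable grade, while Possible means only that the event may be related. Read literally, Minimizing Risks leaves out *possible* events that the stopping rule counts. The grade matters here because Other Foreseeable Risks concedes that effects of disease, transplant and IAC may be hard to separate, so *possible* is a plausible grade. Both referral sentences also cover only SAEs, whereas the section f) rule counts AEs by grade and irreversibility.

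Toxicity is the primary objective. At stake is whether the scheduled board review covers both populations, and whether those asked to evaluate the stopping rules see every event those rules count.

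**Working it through.** **1. The plan's own safety figure.** Section e) gives 10 patients per cohort, closure at more than one event, and at least an 80% chance that the true unacceptable rate is below 30%. With X ~ Binomial(10, 0.30):

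P(X ≥ 2) = 1 − 0.7^10 − 10 × 0.3 × 0.7^9 = 1 − 0.0282 − 0.1211 = 0.851.

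Seeing 0 or 1 event in 10 therefore supports a rate below 30% with about 85% confidence. The exact one-sided 80% upper limits are 14.9% for 0/10 and 27.1% for 1/10. The figure reproduces and is not in dispute.

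**2. Can the board review miss Cohort 2?** Inputs are 10 patients per cohort (Number of Subjects) and a review after k = 2 or 3 patients (section 6c). The documents do not fix enrolment order, so random order is assumed.

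P(no Cohort 2 patient among the first k) = C(10, k) / C(20, k)
- k = 2: 45/190 = 23.7%
- k = 3: 120/1140 = 10.5%

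Treating each enrolment as an independent 50:50 draw gives 0.5² = 25% and 0.5³ = 12.5%, so the conclusion does not depend on which model is used.

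**3. How much could the review show about Cohort 2?** The table gives the chance that it contains at least one Cohort 2 event, averaged over random enrolment order. The event rates are assumed.

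| Cohort 2 event rate | Review at 2 patients | Review at 3 patients | All 10 Cohort 2 patients |
|---|---|---|---|
| 10% | 9.8% | 14.3% | 65.1% |
| 20% | 19.1% | 27.2% | 89.3% |
| 30% | 27.9% | 38.9% | 97.2% |

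The two review columns assume that any event has already occurred by the time of the review. The protocol lists GVHD and graft rejection as long-term toxicities and sets no minimum follow-up before the review, so these values are on the high side.

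**4. The triggers side by side.**

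| Place | Type of event | Attribution |
|---|---|---|
| Minimizing Risks (referral) | SAE | considered likely related |
| 6c, Tests for Safety Data (referral) | SAE | treatment-related, no further limit |
| f), toxicity rule (counted) | irreversible AE, grade 3 or higher | definite, probable or possible |
| e) and f), Cohort 2 (counted) | steroid-refractory GVHD or graft failure | no attribution threshold |

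Two gaps follow. Under Minimizing Risks alone, a *possible* SAE that meets the rule is counted but not referred. Under either referral sentence, an irreversible grade 3 AE not classed as serious is counted but not referred.

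**5. Size of the first gap, if Minimizing Risks alone governs.** Let a share f of qualifying events be graded only *possible*; the documents give no value for f. At a true rate of 30%, the rate of referred events is 0.30 × (1 − f), and the chance that at least 2 of 10 patients have a referred event is:
- f = 0: 85.1%
- f = 25%: 69.5%
- f = 50%: 45.6%
- f = 75%: 17.0%

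These are probabilities of referral, not of stopping. The section f) rule counts *possible* events, so the chance of meeting it stays at 85.1%.

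**The case against.** A reader might infer that Cohort 2 GVHD or graft failure, and events graded *possible*, can escape both board review and the stopping rules. The documents do not support that.

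- **GVHD and graft failure.** A single steroid-refractory GVHD or graft failure in Cohort 2 stops the study, with no attribution threshold and no need for referral. Cumulative data are reviewed weekly. Only a scheduled board review certain to include Cohort 2 is missing.
- **Possible events.** They count toward the section f) rule and are seen at the weekly meetings. No passage makes stopping conditional on biometric review.
- **Referral is not confined to likely SAEs.** Section 6c refers treatment-related SAEs without that word, and section f) glosses treatment-related as definite, probable or possible. Read together, those two sections refer *possible* SAEs. The defect is inconsistent wording, and the referral figures in step 5 apply only if Minimizing Risks is followed alone.
- **One review is inferred from silence.** Section 6c neither says the board meets once nor rules out later review.
- **Seriousness.** Many irreversible grade 3 events may be classed as serious anyway, which would narrow the second gap. The protocol does not define the term, so its size cannot be judged.

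It can also be said that repeating the board review by cohort is a preference in a 20-patient pilot that already has weekly review and strict stopping rules. Those safeguards are real and limit the weight of this point. They do not answer it: the weekly review is by the study groups, and the one scheduled board review can still contain no patient from the cohort of greatest concern. Nor does the broader sentence in section 6c settle the trigger, because Minimizing Risks is the sentence that links biometric evaluation to the stopping rules.

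**Conclusion.** The point holds in two limited parts.

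1. The only board review specified is not tied to cohort and has no scheduled successor. With random enrolment of 10 + 10, it contains no Cohort 2 patient with probability 23.7% (2 patients) or 10.5% (3 patients). Even averaged over all orders, it would contain a Cohort 2 event with probability of only 27.9% or 38.9% at an assumed 30% event rate.
2. The biometric-review trigger is stated in two ways, and neither matches the events counted in section f). This is an inconsistency to reconcile; the stopping rules themselves are intact. The fall in referral probability from 85.1% to between 69.5% and 17.0% is conditional on one sentence being applied alone and on an assumed 25% to 75% share of *possible* events. It should not be quoted as a loss of stopping probability.

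Enrolment order, event rates and the share of *possible* events are assumptions. The change is worth making because toxicity is the primary objective and the cost is small.

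**What to change.** - **Section 6c, Data and Safety Monitoring:** state that the existing board review takes place after the first 2-3 treated patients in each cohort.
- **Minimizing Risks and section 6c, Tests for Safety Data:** use one referral trigger, reconciled with section f), so that every AE counted by the toxicity stopping rule is referred for stopping-rule evaluation: irreversible, grade 3 or higher, and definite, probable or possible. Keep the word *irreversible*; without it, reversible grade 3 events that section f) treats separately would also be referred.
- **While editing these sections:** section e) closes the study for more than one event in either cohort, whereas section f) terminates only that cohort. These passages must also be reconciled.

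The cost is one additional review by the existing board and a wording change. The two main changes alter no dose, schedule, stopping threshold or sample size.
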